1.0 Background

Data from the 2012 National Health Interview Survey indicate that during a 3-month period, 15% of adults reported neck pain. The 12-month prevalence of chronic neck pain is estimated to be between 30%-50%. Neck pain is especially common in adults older than 50 years and is the fourth leading cause of disability in the United States, after back pain, depression, and joint pain. In a 2008 VA study, Dobsha et al. found back and neck pain diagnoses were present in 67% of 401 Veterans. In another VA study, the two most common cervical spine diagnoses were stenosis (50%) and disk herniation (23%). In Veterans with these diagnoses, neck pain was reported by 96%. The impact of chronic neck pain is widespread, exerting negative effects on individuals' physical, psychological, and economic well-being. Chronic neck pain reduces functional status, quality of life, and is associated with deleterious psychological outcomes, including depression and anxiety. Chronic neck pain is a major reason for health care utilization, accounting for more than 10 million ambulatory medical visits per year. The economic impact of this utilization is significant.

Guidelines highlight a wide range of treatment options for chronic neck pain. In clinical practice, conventional treatments such as medications and physical therapy are most widely used. However, systematic reviews conclude there is still limited evidence for the effectiveness of these treatments for neck pain, relative to low back pain, and current therapies show only modest effect sizes. The mainstay of chronic neck pain treatment is non-steroidal anti-inflammatory drugs (NSAIDs), but NSAIDs often provide suboptimal pain relief, especially when used as mono-therapy, and their adverse effects, such as gastrointestinal, renal, and cardiovascular complications, are well known. Opioids for chronic neck pain are controversial for several reasons. First, their long-term efficacy is questionable. Second, opioids are associated with several problematic side effects. Third, opioids have potential for misuse, abuse, and addiction. Fourth, between 1999 and 2008, the rate of prescription opioid overdose deaths in the US raised four-fold. Thus, when medications and physical therapy fail to relieve pain, Veterans frequently live with chronic, often debilitating, pain. Clearly, effective and safer treatments to improve the management of neck pain are needed.

The National Center for Complementary and Integrative Health (NCCIH, formerly NCCAM) defines complementary health approaches as practices or products of non-mainstream origin. Patient demand for these approaches (previously termed complementary and alternative medicine, CAM) is high. More than 30% of US adults use complementary health care approaches outside of, or integrated within, conventional treatment. Fifty-eight percent of older adults surveyed used some type of alternative treatment. Pain is the primary reason individuals turn to complementary treatments. After low back pain, neck pain is the second most common pain condition for complementary health use. Massage is the second (after chiropractic) most commonly used complementary treatment for neck pain. Complementary health approaches are especially popular and in high demand by Veterans. In a VA study, 82% of Veterans reported use of at least one complementary therapy and nearly all (99%) were willing to try such approaches for pain. Of all complementary health approaches, massage was the most preferred by Veterans. Massage's popularity derives from its patient-centered and healing-oriented approach and emphasis on the therapeutic relationship.

Safer alternatives to conventional pain treatments such as NSAIDS and opioids are needed, especially in older adults. [name], Director of NCCIH stated: "The need for nondrug treatment options (for pain) is a significant and urgent public health imperative." Experts also argue that clinicians and patients need to reduce reliance on pharmacological treatment. It is in this context the VA implemented the high-priority, Opioid Safety Initiative (OSI). The OSI grew out of accumulating evidence that some opioid use is unsafe and may be

contributing to harm for Veterans. In addition to reducing use of high-dose (> 200mg a day) opioids and concomitant opioids and benzodiazepines, a major goal of the OSI is to provide safer alternatives for treating chronic pain. To accomplish this latter goal, VA facilities are being encouraged to implement programs that improve access to complementary health approaches, like massage therapy. Existing studies show massage is safe for all ages--it has few risks if it is used appropriately, and serious adverse effects are rare.

In a review of complementary health approaches for neck pain, massage reduced pain and/or disability more than usual medical care (such as NSAIDs and exercise), physical therapy, or no treatment. Other systematic reviews have shown massage to be effective in the short-term for neck pain, but long-term benefits are unclear. Furthermore, massage is frequently perceived by patients as helpful. In a national survey, almost two-thirds (61%) of individuals with neck pain who used both complementary and conventional treatments perceived complementary therapies to be more helpful, whereas only 6% perceived conventional treatments to be better. A Cochrane review rated the overall quality of most massage trials for neck pain as poor, limited by small samples and lack of detail in published reports. However, recent studies by Sherman have set the standard for methodologically rigorous massage trials for chronic neck pain. In one trial, patients (N = 64) randomized to 10 weeks of massage were much more likely to achieve clinically meaningful improvements for neck pain disability compared to patients randomized to a pain self-care book. In a larger trial (N = 228), Sherman's group found that patients who received 60-minute massage sessions, 1 to 3 times weekly were more likely to reach clinically meaningful improvements on neck pain disability and pain intensity compared to patients in the control arm. In a follow up study, designed to evaluate a longer treatment period for massage, neck-related dysfunction and pain severity were assessed at 12 and 26 weeks. Patients who received booster doses of massage had improvements in both dysfunction and pain severity at 12 weeks but nonsignificant changes at 26 weeks.

Massage is theorized to work through a variety of mechanisms to relieve pain. These mechanisms include: 1) increased local blood circulation; 2) improved muscle tone; 3) increased joint flexibility; 4) heightened relaxation response; and 5) changed neuroendocrine and inflammatory status implicated in pain generation and sensitivity.

Despite its safety and potential benefits, the expense associated with massage therapy makes it inaccessible to most Veterans. The national average cost for a massage is approximately \$60/hour, but varies significantly by region (urban areas are generally more expensive), setting (e.g., fitness clubs) and therapist training. Massage therapy is primarily an out-of-pocket expense that is rarely covered by health insurance and not affordable to most Veterans. While massage therapy is offered at some VA care settings it is not widely available to Veterans. While one study showed higher costs for massage compared to primary care for low back pain,⁴ the cost-effectiveness of massage for neck pain has not been examined thoroughly.

Teaching informal care allies to provide massage (care ally -delivered massage) has been most commonly applied and found effective for patients with cancer. care ally -delivered massage has also been tested in the context of pediatric, obstetrical, and long-term care settings for dementia. Kozak et al demonstrated the feasibility of caregiver-given massage in 27 caregiver-Veteran dyads and found significant decreases in pain, stress/anxiety, and fatigue for Veterans with cancer (mean age 63.8 ± 10.2 years). In a larger study, Collinge recruited 97 patient/caregiver dyads (patient mean age 54.7 (SD 11.6), range 24-78 years; caregivers age range 18-82 years) to practice massage. The intervention, compared to attention control, led to decreases in patients' pain, depression, and other cancer-related symptoms. In addition, caregivers benefitted from doing active, hands-on massage. To our knowledge, care ally -

delivered massage has not been tested in Veterans with chronic non-cancer pain. We believe this is an important research gap that our study aims to fill. Caregiver-delivered massage is Veteran-centered and has promising preliminary data and implementation potential to be applied across VA since it can address system and Veteran-level barriers.

2.0 Rationale and Specific Aims

Study Aims:

- 1) To compare the effect of a massage intervention (therapist-treated massage) vs. control on pain-related disability**
- 2) To compare the effect of a massage intervention vs. control on secondary outcomes, including pain severity, health-related quality of life, depression, anxiety, and stress**
- 3) To examine the implementation potential of the massage intervention, including facilitators and barriers, treatment and adherence, and intervention costs.**

3.0 Inclusion/Exclusion Criteria

Veterans will be eligible if they have:

1) chronic neck pain for 6 months or longer	3) access to a working telephone
	4) the ability and willingness to attend treatments
2) NDI score ≥ 10	

Exclusion criteria will include:

1) neck pain secondary to vertebral fracture or metastatic cancer	10) moderate to severe cognitive impairment or dementia or TBI (as indicated in medical records)
2) complex neck pain (e.g., cervical radiculopathy or recent whiplash injury in the past 3 months)	11) pending neck surgery
3) potential contraindication for massage (e.g., hypersensitivity to touch)	12) involvement in ongoing pain trials or massage study
4) any professional massage therapy within the last 1 month or massage therapy specifically for neck pain within the past 3 months *excluding physical therapy, chiropractor, salon/hairdresser etc.	13) Hospitalized in the last 6 months for congestive heart failure
5) Hospitalized for psychiatric reasons in the last 3 months	14) Had a heart attack in the last 6 months
6) Had a stroke or TIA in the last 6 month	
7) Has been hospitalized for COPD or emphysema in the last 6 months	
8) Had a fracture or broken bone in neck during last 6 months	
9) active suicidal ideation (as indicated in medical records)	16) Active treatment for cancer other than skin cancer or palliative care for cancer

Access to a telephone is required because most of the outcome assessments will be conducted via phone. Exclusion criteria will be determined during the baseline eligibility survey conducted by our study team (not the patient's providers) and are designed to eliminate potential participants for whom the proposed interventions are inappropriate or for whom there may be disincentives for improvement.

As of the September 22, 2021 amendment, the TOMCATT study team is prioritizing patients for enrollment who have received a vaccine against COVID-19. The nature of the study treatment dictates that those enrolled in the TTM arm will need to have prolonged, in-person interaction with the massage therapists twice per week for 12 weeks. Therefore, we are prioritizing the enrollment of vaccinated participants to improve the safety of our research team and our study participants.

To determine if potential participants have received a vaccine against COVID-19, we will either confirm vaccination status in the medical record (if documented), or ask for this information on via recruitment letter and eligibility interview.

4.0 Enrollment/Randomization

Enrollment

Providers will be informed of TOMCATT study details and will be asked to provide signed approval so that our research team may contact their potentially eligible patients for participation in the study. The study will recruit providers at the Richard L. Roudebush VAMC and surrounding CBOC's. The research team, not the providers, will determine eligibility by applying the inclusion/exclusion criteria to potential participants during a comprehensive "eligibility interview." Potential participants will be identified by querying the VA's electronic medical record system, CPRS (Computerized Patient Record System), to create a master list of Veterans who meet the following criteria: 1) ICD 9/10 codes that identify neck pain, osteoarthritis, and musculoskeletal pain

A recruitment letter, signed by their provider, will be mailed to qualifying Veterans to describe the study. If a Veteran does not have a PCP, a separate letter signed by [name] will be mailed instead. Potential participants will be contacted by phone within a week after receipt of the letter to assess eligibility and determine their interest in participating. If the Veteran is eligible, an appointment will be scheduled to obtain an IRB-approved, VA signed informed consent statement and HIPAA authorization from those who desire to participate. Consent may be collected in-person, or via DocuSign accompanied by a virtual (Microsoft Teams or phone) conversation to explain consent and answer any questions about the study. The baseline interview and assessments will be conducted by a research assistant. A second method, if needed, will be in-clinic contact of potential participants by cross-referencing the CPRS list with the weekly appointment roster for each participating VA provider. A third method is self-referral by patients responding to a study advertisement displayed in hospital elevators and primary care and rehabilitation clinics. Brochures will also be placed throughout the community in places Veterans are likely to visit. This will include American Legion posts, DVA chapters, military recruiting stations, etc.

To increase recruitment pool, an email blast will be sent out to an official VA mass email list that the recipients have consented to being on. This email group is specifically targeted towards veterans enrolled in healthcare in Indiana. The address is a no-reply address and veterans will be given only phone numbers for staff to protect their privacy.

To further increase recruitment, a single-slide informative visual will be placed on televisions in the Roudebush VAMC. This visual will include a graphic, a brief description of who would be eligible, a brief description of the commitment the study entails for the veteran, a brief description of the protocol, and contact information for the study team.

In addition to these measures, the study team will place lockboxes in the primary care clinics with a small advertisement for the study, using the same slide from the television ad.

The interested participants will be able to fill out an NDI at and place it in the lockbox. Study staff will collect these at the end of the day.

Randomization

Stratified and blocked randomization will be performed. After providing written-informed consent and completing their baseline interview, participants will be randomized to one of 2 arms:

- 1) Therapist-treated massage (TT-M)
- 2) Waitlist control (WL-C)

The randomization process will be directed by [name] (statistician) using statistical software with a random-number generator to create a list of group assignments before study recruitment begins. Randomization will be stratified by sex (men vs. women). Within strata, randomization with block sizes of 4 will be executed to ensure balance. Once an eligible participant has been screened, has signed informed consent, and has completed the baseline measures, the research assistant or project coordinator will pull the next sealed envelope. The randomization program locates the first unassigned record in the randomization list and assigns the participant to the group designated in that record. The participant identifier and date are written to the record. [name] will remain blinded to group assignment.

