New modification sample size: For the comparison of the TT-M and the waitlist control group (WL-C) we need 100 patients per group ($N = 200$) by 3 months to have 80% power to detect a 0.4 SD difference in change in NDI from baseline between TT-M and control with Type I error = 0.05 for the comparison of interest: TT-M vs WL-C. All analysis will be conducted under the intention-to-treat principle. Sample size was derived based on an independent two-sample t-test which is conservative compared to the contrast from our proposed linear mixed model.

Previously we assumed a total attrition for the TTM and WL-C arm of $(27+20)/(98+99) = 47/197 = 24\%$, thus we sought to enroll a Total $N = 264$ ($200/.76$) or 132 per group in the TT-M and WL-C study groups. We will now enroll Total $N = 296$ ($264 + 16 \times 2$) so that we will

have an additional 16 in the TTM arm to account for the 16 that were paused due to COVID but will also maintain the current randomization allocation. For IRB purposes, we will continue to recruit to reach at most N = 308 this would increase the 16 COVID paused to also account for potential 24% attrition (16/.76 = 22 per group). However, this is not necessarily required as the COVID paused will still be included in the linear mixed model up until their one month assessment. This should allow us to reach our sample size of 100 per group to complete the 3 month assessment.

Data analysis: Baseline characteristics of TOMCATT sample

As an RCT, we expect characteristics of study participants to be balanced across the two study arms. We will compare all baseline demographic and clinical characteristics between the treatment groups using the appropriate test (ie, ANOVA, Kruskal-Wallis test, or Chi-square test). Variables found to significantly differ will be included in subsequent regression models.

Main analysis (Aim 1) of the primary outcome (NDI total score)

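### A fixed block size of 4 within sex strata, with arms that cannot be masked, weakens allocation concealment, and two assignment devices are described without being reconciled

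*Combined protocol and SAP*

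**What the plan says.** All of this is in Section 4.0 (Enrollment/Randomization) of the combined protocol and SAP, unless noted.

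- **Scheme.** After consent and baseline, "participants will be randomized to one of 2 arms": therapist-treated massage or waitlist control. The list is stratified by sex, and "Within strata, randomization with block sizes of 4 will be executed to ensure balance". The statistician prepares it before recruitment starts.
- **Who does what.** "The research team, not the providers, will determine eligibility by applying the inclusion/exclusion criteria to potential participants". A research assistant conducts the baseline interview. Once screening, consent and baseline are complete, "the research assistant or project coordinator will pull the next sealed envelope".
- **Second device.** The next sentence reads: "The randomization program locates the first unassigned record in the randomization list". The text does not say how the envelope and the program relate.
- **Blinding.** One redacted person stays blinded to group. No blinding is stated for enrolling staff.
- **Not stated.** Whether the block size is withheld from recruiting staff, whether envelopes are opaque, numbered and kept by stratum, and who holds them.
- **Ratio.** 1:1 is not written out. It follows from equal targets in Section 8.0 ("or 132 per group in the TT-M and WL-C study groups").

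**The concern.** With one known block size, the end of each block can be deduced from its beginning. Staff who arrange massage sessions see who was assigned to massage, and with only two sex strata a running tally is easy to keep. Section 5.0 has the study team use the same email system for enrollment and for massage schedules, so nothing separates recruiting staff from past assignments.

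Foreknowledge could matter in two ways. Staff could, without intending it, bring forward or delay a participant's final enrollment step. Section 3.0 leaves some discretion here: it asks for ability and willingness to attend treatments, and it prioritizes vaccinated patients because of in-person contact in the massage arm. Staff could also administer the baseline NDI differently. The primary contrast is change in a self-reported NDI, so a baseline score shaped by the expected arm would enter that contrast directly.

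**Working it through.** The plan gives no predictability figure to reproduce. Its sample-size figures (100 per group, then 264, 296 and 308) do reproduce and are not in question here.

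**Inputs.** Block size 4, two arms and two sex strata (Section 4.0); 1:1 ratio (inferred from Section 8.0). Assumed observer: knows the block size, where blocks start and every earlier same-sex assignment.

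**1. Certain just before the envelope is pulled.** The six equally likely blocks (M = massage, W = waitlist) are MMWW, MWMW, MWWM, WMMW, WMWM and WWMM. The fourth position is always determined. The third is determined only in MMWW and WWMM.

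- Determined positions: 2 + 1 + 1 + 1 + 1 + 2 = 8 of 24 = 1/3 (33.3%).
- By position: (0 + 0 + 1/3 + 1)/4 = 1/3.
- For a fixed block of size B the share is 1/(B/2 + 1): 25% for B = 6 and 20% for B = 8.

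Stratification does not change the fraction. It only sets how many tallies must be kept.

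**2. Best-guess accuracy.** By position: 1/2, 2/3, 2/3 and 1. The mean is (1/2 + 2/3 + 2/3 + 1)/4 = 17/24 = 70.8%, against 50% with no information.

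**3. Certain earlier in the process.** Suppose other same-sex participants are randomized between the moment of judgement and the envelope.

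- One in between: only position 4 can be known, and only when the first two assignments match (probability 1/3). The share is (1/3)/4 = 1/12 = 8.3%.
- Two or more in between: 0%.

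Illustration for the eligibility call, using the only stated recruitment rate (12 per month, Section 8.0). Assume 7 days from call to randomization, 30.4 days per month and random arrivals. Neither the gap nor the sex split is in the document. With m = 12 × (stratum's share of enrollment) × 7/30.4, the certain share is e^(−m) × (1/3 + m/12):

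| Stratum's share of enrollment | m | Certain at the call |
|---|---|---|
| 10% | 0.28 | 27% |
| 50% | 1.38 | 11% |
| 90% | 2.49 | 4.5% |

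**4. Effect of varying block sizes.** Simulated with an observer who knows the set of sizes but not their order (148 per stratum, that is 296/2, and 800 runs). As a check, fixed blocks of 4 gave 33.4% certain and 70.8% guessable.

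| Block sizes | Certain | Guessable |
|---|---|---|
| 4 and 6 | 5.4% | 69% |
| 4, 6 and 8 | 2.1% | 68% |

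A separate simulation of 4/6/8 gave 2.5% and 68%.

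**The case against.** The strongest reply is that assignment sits in a sealed envelope opened only after screening, consent and baseline. A reader might infer that allocation is not concealed at all. The document does not support that: the envelope is a concealment step, and at that point eligibility, consent and baseline are complete. What remains is that an envelope hides its contents, not what earlier assignments imply.

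Other stronger readings also fail:

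- **That one third are known at screening.** The full third applies only if no same-sex participant is randomized in between. A scheduled consent visit and a baseline interview separate the call from the envelope, so the share at the call is usually lower (step 3).
- **That one small team sees every earlier assignment.** The document does not say this. It names a research team, a research assistant and a project coordinator, who may be different people, and it does not show that anyone keeps a tally. It also does not prevent it.
- **A count of affected patients.** Taking 296 − 197 = 99 and a third of that gives about 33. But 197 comes from the superseded attrition calculation in Section 8.0, and the current text gives no enrollment to date.
- **That one third applies to the whole trial.** Section 5.0 records the removal of a care-ally arm. Equal three-arm allocation cannot balance in blocks of 4, so the early block structure is unknown.
- **That analysis offers no protection.** Section 8.0 adds baseline variables that differ significantly between arms to the models. That is partial protection.

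It also stands that varying sizes barely reduce guessing, and that no bias in NDI has been quantified.

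**Conclusion.** Concealment is weakened and under-described, not absent. For two-arm 1:1 blocks of 4, an expected one third of assignments are certain and 71% guessable just before the envelope is pulled. The exposure lies mainly in the baseline interview and late timing of enrollment. This rests on staff knowing the block size, the block starts and the earlier same-sex assignments, which the document neither states nor rules out. Nothing suggests that staff have acted on such knowledge. The unreconciled envelope and program wording needs correcting whatever view is taken of predictability. The case for change rests on low cost and on removing most of the certainty, not on a demonstrated bias.

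**What to change.** For any remaining randomizations:

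1. The statistician generates a new list within each sex stratum, with block sizes varying at random (for example 4, 6 and 8), starting after each open block of 4 is completed. The sizes are kept in a restricted document and not disclosed to recruiting staff.
2. Each assignment is released by one device only, the randomization program, after the baseline record is locked. The envelope wording is deleted.
3. Section 4.0 states who holds the list and that recruiting staff have no access to it.

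For assignments already made, the sponsor should report which device and block structure were used, including during the three-arm phase. It should also compare baseline NDI by arm in predictable and unpredictable positions.

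**Cost.** One new list and a short amendment, with no extra patients. Stopping inside a block of 8 can leave an imbalance of up to 4 per stratum. If an open block of 4 is abandoned instead of completed, that adds up to 2, for a total of up to 6. Completing it leaves at most 3 more assignments per stratum under the old scheme. If enrollment has closed, only the wording correction and the reporting apply.
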